#### **12.6.2 Attribution**

Attribution is the relationship between an adverse event or serious adverse event and the study treatment. Attribution will be assigned as follows:

- **Definite** – The AE is clearly related to the study treatment
- **Probable** – The AE is likely related to the study treatment
- **Possible** – The AE may be related to the study treatment
- **Unlikely** - The AE is doubtfully related to the study treatment
- **Unrelated** - The AE is clearly NOT related to the study treatment

### **12.7. Reporting Procedures**

#### **12.7.1 Specific Instructions for Recording Adverse Events**

Investigators should use correct medical terminology/concepts when reporting AEs or SAEs. Avoid colloquialisms and abbreviations. All adverse events will be captured on the appropriate study-specific case report forms (CRFs).

#### **12.7.2 Diagnosis versus Signs and Symptoms**

If known at the time of reporting, a diagnosis should be reported rather than individual signs and symptoms (e.g. record only liver failure or hepatitis rather than jaundice, asterixis, and elevated

transaminases). However, if a constellation of signs and/or symptoms cannot be medically characterized as a single diagnosis or syndrome at the time of reporting, it is acceptable to report the information that is currently available. If a diagnosis is subsequently established, it should be reported as follow-up information.

#### **12.7.3 Deaths**

All deaths that occur during the protocol-specified AE reporting period, regardless of attribution, will be reported to the appropriate parties. When recording a death, the event or condition that caused or contributed to the fatal outcome should be reported as the single medical concept. If the cause of death is unknown and cannot be ascertained at the time of reporting, report "Unexplained Death." Deaths that occur during the protocol specified adverse event reporting period that are attributed by the investigator solely to progression of disease should be recorded only in the study CRF.

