  - A life-threatening bleeding event which results in urgent intervention and admission to an Intensive Care Unit
- Any Grade 5 hematologic or non-hematologic toxicity excluding death due to disease progression

3) **DLT for inability to initiate Cycle 2 within 4 weeks of scheduled treatment**

- Due to slow recovery from adverse event classified by the investigator as possibly, probably or definitely related to CB-839, or to the combination of CB-839 + panitumumab/irinotecan and failure to meet protocol-defined retreatment criteria.

Subjects who have experienced a DLT do not automatically require discontinuation of protocol-indicated treatment, unless the nature or severity of the DLT is also an adverse event that would require permanent discontinuation of study as elsewhere defined by the protocol. Rather, a patient who has experienced a DLT should be evaluated for consideration of an appropriate dose hold or dose modification which, if consistent with the protocol, would allow continued dosing under revised circumstance.

Dose reductions are not allowed during the DLT window for a patient to count in dose-escalation decisions. After Cycle 1, dose reductions or interruptions for adverse events may take place at any time as otherwise consistent with the protocol.

For purpose of ensuring appropriate opportunity to determine the maximum tolerated dose (MTD) of CB-839 in combination with panitumumab + irinotecan, a subject who is withdrawn from the study prior to

completing the DLT assessment window (i.e. first 28 days after initiating protocol-indicated therapy on Cycle 1, Day 1) for reasons other than a DLT will not be considered evaluable for DLT and will be replaced.

Additionally, if a patient discontinues study treatment for reasons clearly not related to study treatment (in the judgement of the investigator), after completing less than 75% of scheduled oral doses of CB-839 and/or less than 2 planned infusions of panitumumab and 2 planned infusions of irinotecan over the first 28 days after initiating protocol-indicated treatment on Cycle 1, Day 1, then that patient will be considered not evaluable for response to overall protocol-indicated treatment and may be replaced with a new patient.

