## **12. SAFETY REPORTING OF ADVERSE EVENTS**

### **12.1. General**

Safety assessments will consist of monitoring and appropriate reporting AEs and SAEs that are considered possibly, probably or definitely related to the **investigational treatment (i.e. to CB-839, or to the combination of CB-839 + panitumumab/irinotecan) and research F-FSPG PET/CT scans**, all events of death, and any study-specific issue of concern.

Adverse event collection and reporting is a routine part of every clinical trial. Each adverse event will be graded according to the NCI's Common Terminology Criteria for Adverse Events (NCI CTCAE), Version 4.03, dated June 14, 2010, currently locatable via the following URL:

[http://evs.nci.nih.gov/ftp1/CTCAE/CTCAE\\_4.03\\_2010-06-14\\_QuickReference\\_8.5x11.pdf](http://evs.nci.nih.gov/ftp1/CTCAE/CTCAE_4.03_2010-06-14_QuickReference_8.5x11.pdf)

For events not listed in the CTCAE, severity will be designated as mild, moderate, severe or life threatening, or fatal which respectively correspond to Grades 1, 2, 3, 4, and 5 on the NCI CTCAE, with the following definitions:

- **Mild:** An event not resulting in disability or incapacity and which resolves without intervention;
- **Moderate:** An event not resulting in disability or incapacity but which requires intervention;
- **Severe:** An event resulting in temporary disability or incapacity and which requires intervention;
- **Life-threatening:** An event in which the patient was at risk of death at the time of the event;
- **Fatal:** An event that results in the death of the patient.

Information on all adverse events, whether serious or not, whether reported by the participant, directly observed, or detected by physical examination, laboratory test or other means, will be collected, recorded, followed and reported as described in the following sections.

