### 12.5.2 Serious adverse event (SAE)

A serious adverse event is an undesirable sign, symptom or medical condition which:

- is fatal or life-threatening;
- requires or prolongs inpatient hospitalization;
- results in persistent or significant disability/incapacity;
- constitutes a congenital anomaly or birth defect; or
- jeopardizes the participant and requires medical or surgical intervention to prevent one of the outcomes listed above.

Events **not** considered to be serious adverse events are hospitalizations for:

- routine treatment or monitoring of the studied indication, not associated with any deterioration in condition, or for elective procedures
- elective or pre-planned treatment for a pre-existing condition that did not worsen
- emergency outpatient treatment for an event not fulfilling the serious criteria outlined above and not resulting in inpatient admission
- respite care

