#### **12.7.9 Serious Adverse Events**

All serious adverse events, regardless of causality to study drug, will be reported to the Principal Investigator and/or the Study Coordinator at each institution, and also to the Coordinating Center.

All serious adverse events must be reported to the Coordinating Center within 24 hours of the investigator becoming aware of the event. Events should be reported using the Vanderbilt SAE form, located in the packet of supplemental forms. This form must be fully completed and emailed (preferred), faxed, or scanned to:

Follow-up information must also be reported within 24 hours of receipt of the information by the investigator.

The Coordinating Center will disseminate information regarding serious adverse events to the participating sites as described in FDA guidance only in the case that the event(s) is/are unexpected, and is/are believed to be related (i.e., possibly, probably or definitely) to the study device/medication. The Coordinating Center will be responsible for reporting of events to the FDA and supporters, as appropriate (outlined below).

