### **13.3. Auditing and Monitoring**

The Vanderbilt-Ingram Cancer Center (VICC) oversees patient safety and data monitoring for its investigator-initiated and NIH-NCI funded clinical trials through its Data and Safety Monitoring Committee (DSMC). The purpose of the DSMC is to ensure the efficient implementation and management of VICC Data and Safety Monitoring Plan (DSMP). The Committee maintains authority to intervene in the conduct of studies as necessary to ensure clinical research performed at VICC or by additional sites for VICC Investigator Initiated Trials, achieves the highest quality standards.

The VICC DSMC meets on a quarterly basis and ad hoc to discuss data and safety monitoring of clinical trials and to oversee the VICC DSMP. Internal audits for compliance with adverse event reporting, regulatory and study requirements, and data accuracy and completion are conducted according to the VICC DSMP according to study phase and risk. The committee reviews all serious adverse events (SAE) on Vanderbilt sponsored investigator-initiated studies on a quarterly basis and provides DSMC SAE review reports to the Vanderbilt IRB.

The trial additionally will be monitored by the VICC Multi-Institutional Coordinating Center. The actual frequency of monitoring will depend on the enrollment rate and performance of the site. Monitoring will be conducted through onsite and/or remote monitoring, teleconferences with the Investigator and site staff, and appropriate communications by mail, fax, email, or telephone. The purpose of monitoring is to ensure that the study is conducted in compliance with the protocol, standard operating procedures (SOPs), and other written instructions, and to ensure the quality and integrity of the data.

During scheduled monitoring visits, investigators and the investigational site staff must be available to discuss the progress of the trial, make necessary corrections to case report form entries, respond to data clarification requests, provide required regulatory documents, and respond to any other trial-related inquiries of the monitor.

In addition to the above, the FDA may review the conduct or results of the study at the investigational site.

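### Section 12.7.3 requires every death in the reporting period to be reported, then confines deaths attributed solely to progression to the CRF; other sections make every fatal event a reportable SAE, and none says which rule prevails

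*Combined protocol and SAP*

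**What the plan says.** Section 12.7.3 gives two instructions. The first is general: "All deaths that occur during the protocol-specified AE reporting period, regardless of attribution, will be reported to the appropriate parties". The last sentence covers deaths in the same period that are "attributed by the investigator solely to progression of disease should be recorded only in the study CRF".

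Four other parts of Section 12 bear on the same deaths:

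- Section 12.1 includes in the safety assessments "all events of death, and any study-specific issue of concern", with no exception for progression.
- Section 12.5.2 makes an event serious if it "is fatal or life-threatening". Its list of exclusions covers certain hospitalizations, outpatient emergency care and respite care. Progression is not on it.
- Section 12.7.9 states: "All serious adverse events, regardless of causality to study drug, will be reported to the Principal Investigator and/or the Study Coordinator", and also to the Coordinating Center, within 24 hours of awareness.
- Section 12.7.13 sends all SAEs, whatever their cause, in parallel to the supplier's pharmacovigilance agent.

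On oversight, Section 13.3 says of the DSMC: "The committee reviews all serious adverse events (SAE) on Vanderbilt sponsored investigator-initiated studies on a quarterly basis". The reporting period (Section 12.1) runs through 28 days after the last dose.

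**The concern.** The two instructions in 12.7.3 cannot both be followed for a death judged to be due solely to progression, unless reporting to the appropriate parties is taken to mean no more than a CRF entry. The other sections do not allow that reading.

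What is at stake is the route the death takes. The 24-hour form, the supplier report and the DSMC's case review are all triggered by an event being handled as an SAE. Expedited FDA reporting (12.7.11 and 12.7.12) depends on the sponsor-investigator's own judgement of relatedness, and a death that never arrives as an SAE may not prompt it. The label that takes a death off this route is the investigator's attribution, and no section requires anyone to review that label. In refractory metastatic disease most deaths will at least be candidates for it, so the rule should be unambiguous.

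**Working it through.** **Passages side by side, for one case.** Take a Phase II patient who dies 20 days after the last dose. The investigator attributes the death solely to progression.

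| Source | What happens to this death |
|---|---|
| 12.7.3, first sentence | Reported to the appropriate parties |
| 12.7.3, last sentence | CRF only |
| 12.1 | Within the deaths listed for reporting |
| 12.5.1 and 12.5.2 | A worsening medical condition is an adverse event even if unrelated to the study; a fatal one is serious; no exclusion applies |
| 12.7.9 | SAE to the Coordinating Center within 24 hours, whatever the cause |
| 12.7.13 | SAE to the supplier's agent, whatever the cause |
| 13.3 | Seen by the DSMC in its quarterly review only if handled as an SAE |

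The last sentence of 12.7.3 stands alone against the first sentence and four other sections. None of them cross-refers to it, and no order of precedence is given.

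**Scale.** The documents do not say what share of deaths would be attributed solely to progression, so the number affected cannot be calculated. A ceiling can be illustrated from Section 15, which expects median PFS of 1.9 months and median OS of 6.4 months with exponential survival.

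Expected events among n patients by time t: n × (1 − 2^(−t/median)).

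The plan's own figures reproduce first:
- Deaths by 12 months: 29 × (1 − 2^(−12/6.4)) = 21.1; the plan says 21.
- Progressions by 12 months: 29 × (1 − 2^(−12/1.9)) = 28.6; the plan says 29.

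For all-cause deaths in the reporting window, 28 days = 28/30.44 = 0.92 months, and time on treatment must be assumed:

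| Assumed time at risk before the 28-day tail (months) | Total t (months) | Probability of death | Expected deaths of 29 |
|---|---|---|---|
| 0 (no deaths on treatment) | 0.92 | 0.095 | 2.7 |
| 0.92 (one cycle) | 1.84 | 0.181 | 5.2 |
| 1.90 (median PFS) | 2.82 | 0.263 | 7.6 |
| 3.68 (four cycles) | 4.60 | 0.392 | 11.4 |

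These are deaths from any cause in Phase II. Deaths attributed solely to progression are a subset of unknown size. The constant hazard from day 1 is also an assumption. Inclusion is limited to ECOG 0 or 1, so early deaths may be fewer than shown.

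**The case against.** The strongest reply is that 12.7.3 states a general rule and then a specific exception, and that keeping progression deaths out of the SAE stream is a deliberate choice. That would be a fair reading of 12.7.3 alone. It does not survive 12.5.2, 12.7.9 and 12.7.13, which define and route SAEs without regard to cause and carry no matching exception.

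The other side also has points that stand and limit the concern:

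- The carve-out covers only deaths attributed solely to progression, and 12.7.3 asks for any condition that caused or contributed to the death.
- The death remains in the CRF and counts for overall survival.
- A toxicity that led to hospitalization before death is an SAE in its own right (12.7.5).
- A site that follows 12.7.9 literally would report the death anyway.

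Three stronger readings may tempt a reader, and the documents do not support them.

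*That nobody outside the treating team would see the attribution.* The eCRF is centralized (13.1), CRF information and toxicity assessments go to the Coordinating Center (14.6), and the trial is monitored and audited (13.3). What is missing is a required review of the attribution; the record itself stays visible.

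*That the contradiction decides Phase I dose escalation.* The exclusion from DLTs is a separate rule in Section 10.1, "Any Grade 5 hematologic or non-hematologic toxicity excluding death due to disease progression", and it does not conflict with itself. Editing 12.7.3 would not alter it. Section 10.1 also replaces a patient withdrawn before completing the DLT window for reasons other than a DLT. On the natural reading, a progression death in Cycle 1 brings in a new patient with a new outcome, and one DLT in three does not simply become none in three.

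*That fatal liver toxicity is likely to be lost this way.* Liver-test elevation is the most frequent related Grade 3/4 toxicity. However, Section 2.4.2 puts it at about 2% with twice-daily dosing with food and describes it as generally asymptomatic and reversible. Misattribution is possible, but nothing in the documents shows that it is probable.

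**Conclusion.** The contradiction is real and the text should be corrected. For a death in the reporting period judged to be due solely to progression, the protocol gives opposite instructions, and they determine whether the death reaches the 24-hour SAE report, the supplier and the DSMC's SAE review. The effect is inconsistent handling. Certain loss of safety data does not follow, because the death stays in a monitored eCRF.

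No figure can be put on the deaths affected. The illustrative all-cause totals of roughly 3 to 11 among 29 Phase II patients bound the number from above under the stated assumptions about time at risk and constant hazard. They should not be read as the number that turns on this sentence. The textual conclusion rests on none of those assumptions.

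**What to change.** Replace the last sentence of 12.7.3 with one rule consistent with 12.1, 12.5.2, 12.7.9 and 12.7.13. For example: each death from the start of adverse event reporting through 28 days after the last dose is reported as an SAE to the Coordinating Center within 24 hours and to the supplier's agent in parallel, with the investigator's attribution stated, and is included in the DSMC's SAE review. Add that expedited FDA reporting remains limited to unexpected events suspected to be related, as 12.7.11 and 12.7.12 already provide, so deaths judged solely due to progression do not generate expedited reports.

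In Section 15, add a table of deaths within 28 days of last dose by attributed cause. It should cover everyone who received any protocol treatment, because the safety set described there requires at least one cycle and may omit a death during Cycle 1.

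The cost is a wording amendment, one table and a small number of extra SAE forms, which cannot exceed the number of deaths in the window. No treatment, visit or procedure changes.

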#### **12.7.4 Pre-existing Medical Conditions**

A pre-existing medical condition is one that is present at the start of the study. Such conditions should be reported as medical and surgical history. A pre-existing medical condition should be re-assessed throughout the trial and reported as an AE or SAE only if the frequency, severity, or character of the condition worsens during the study. When reporting such events, it is important to convey the concept that the pre-existing condition has changed by including applicable descriptors (e.g., "more frequent headaches").

#### **12.7.5 Hospitalizations for Medical or Surgical Procedures**

Any AE that results in hospitalization or prolonged hospitalization should be documented and reported as an SAE. If a patient is hospitalized to undergo a medical or surgical procedure as a result of an AE, the event responsible for the procedure, not the procedure itself, should be reported as the SAE. For example, if a patient is hospitalized to undergo coronary bypass surgery, record the heart condition that necessitated the bypass as the SAE.

Hospitalizations for the following reasons do not require reporting:

- Hospitalization or prolonged hospitalization for diagnostic or elective surgical procedures for pre-existing conditions,
- Hospitalization or prolonged hospitalization required to allow efficacy measurement for the study, or
- Hospitalization or prolonged hospitalization for scheduled therapy of the target disease of the study.

#### **12.7.6 Pregnancies in Female Patients**

Female patients of childbearing potential will be instructed to immediately inform the investigator if they become pregnant during the study or within 2 months after the last dose of protocol-indicated treatment. Pregnancies should be reported by the site immediately (i.e., no more than 24 hours after learning of the pregnancy) using the Vanderbilt SAE form and submitted via fax or email. Unless otherwise agreed to and approved by the sponsor-investigator, investigator and the IRB, the patient should discontinue protocol-indicated treatment. The investigator or medical designee should counsel the patient, discussing the risks of the pregnancy and the possible effects on the fetus. Monitoring of the patient should continue until conclusion of the pregnancy. Any SAEs associated with the pregnancy (e.g. an event in the fetus, an event in the mother during or after the pregnancy, or a congenital anomaly/birth defect in the child) should be reported.

#### **12.7.7 Pregnancies in Female Partners of Male Patients**

Male patients will be instructed through the informed consent form to immediately inform the investigator if their partner becomes pregnant during the study or within 2 months after completing protocol-indicated treatment. Male patients who received study treatment should not attempt to father a child until 2 months after stopping study treatment. Any pregnancies should be reported by the site immediately (i.e., no more than 24 hours after learning of the pregnancy) using the Vanderbilt SAE form and submitted via fax or email. Attempts should be made to collect and report details of the course and outcome of any pregnancy in the partner of a male patient exposed to study drug.

The pregnant partner may be asked to sign an Authorization for Use and Disclosure of Pregnancy Health Information to allow for follow-up on her pregnancy. Once the authorization has been signed, the will provide additional information on the course and outcome of the pregnancy. An investigator or medical designee who is contacted by the male patient or his pregnant partner may provide information on the risks of the pregnancy and the possible effects on the fetus, to support an informed decision in cooperation with the treating physician and/or obstetrician.

#### **12.7.8 Post-Study Adverse Events**

The investigator should expeditiously report any SAE occurring after a patient has completed or discontinued study participation if attributed to previous protocol-indicated CB-839 or CB-839 + panitumumab/irinotecan exposure. If the investigator should become aware of the development of cancer or a congenital anomaly in a subsequently conceived offspring of a female patient who participated in the study, this should be reported as an SAE.

#### **12.7.9 Serious Adverse Events**

All serious adverse events, regardless of causality to study drug, will be reported to the Principal Investigator and/or the Study Coordinator at each institution, and also to the Coordinating Center.

All serious adverse events must be reported to the Coordinating Center within 24 hours of the investigator becoming aware of the event. Events should be reported using the Vanderbilt SAE form, located in the packet of supplemental forms. This form must be fully completed and emailed (preferred), faxed, or scanned to:

Follow-up information must also be reported within 24 hours of receipt of the information by the investigator.

The Coordinating Center will disseminate information regarding serious adverse events to the participating sites as described in FDA guidance only in the case that the event(s) is/are unexpected, and is/are believed to be related (i.e., possibly, probably or definitely) to the study device/medication. The Coordinating Center will be responsible for reporting of events to the FDA and supporters, as appropriate (outlined below).

